3. PARTICIPANT SELECTION

3.1 Eligibility Criteria

Participants must meet the following criteria on screening examination to be eligible to participate in the study:

- 3.1.1 Recipients of 7-8/8 HLA matched adult donor allogeneic stem cell transplantation with myeloablative or non-myeloablative conditioning regimens.
- 3.1.2 Participants must have steroid-refractory cGVHD. Steroid-refractory cGVHD is defined as having persistent signs and symptoms of cGVHD (Appendix D; section 17.4) despite the use of prednisone at ≥ 0.25 mg/kg/day (or 0.5 mg/kg every other day) for at least 4 weeks (or equivalent dosing of alternate corticosteroids) without complete resolution of signs and symptoms. Patients with either extensive chronic GVHD or limited chronic GVHD requiring systemic therapy are eligible.
- 3.1.3 Stable dose of corticosteroids for 4 weeks prior to enrollment. Exception permitted with overall PI approval.
- 3.1.4 No addition or subtraction of other immunosuppressive medications (e.g., calcineurin-inhibitors, sirolimus, mycophenolate-mofetil) for 4 weeks prior to enrollment. The dose of immunosuppressive medicines may be adjusted based on the therapeutic range of that drug
- 3.1.5 Patient age ≥ 18 years old. Because no dosing or adverse event data are currently available on the use of IL-2 in participants <18 years of age, children are excluded from this study.
- 3.1.6 Estimated life expectancy greater than 3 months.
- 3.1.7 ECOG performance status 0-2 (Appendix A; section 17.1).
- 3.1.8 Participants must have adequate organ function as defined below:
 - Hepatic: Adequate hepatic function (total bilirubin <2.0 mg/dl-exception permitted in patients with Gilbert's Syndrome; AST (SGOT)/ALT (SGPT) $\leq 2x$ ULN), unless hepatic dysfunction is a manifestation of presumed cGVHD. For patients with abnormal LFTs as the sole manifestation of cGVHD, documented GVHD on liver biopsy will be required prior to enrollment. Abnormal LFTs in the context of active cGVHD involving other organ systems may also be permitted if

CONFIDENTIAL

This document is confidential. Do not disclose or use except as authorized.

Phase II ECP and IL-2 for chronic GVHD

Version 2.0; August 15, 2016

the treating physician documents the abnormal LFTs as being consistent with hepatic cGVHD, and a liver biopsy will not be mandated in this situation.

- Renal: Serum creatinine within normal institutional limits or creatinine clearance ≥ 60 mL/min/1.73 m² for participants with creatinine levels above institutional normal.
- Pulmonary: FEV1 $\geq 50\%$ or DLCO(Hb) $\geq 40\%$ of predicted, unless pulmonary dysfunction is deemed to be due to chronic GVHD.
- Adequate bone marrow function indicated by ANC $>1000/\text{mm}^3$ and platelets $>50,000/\text{mm}^3$ without growth factors or transfusions
- Cardiac: No myocardial infarction within 6 months prior to enrollment or NYHA Class III or IV heart failure, uncontrolled angina, severe uncontrolled ventricular arrhythmias, or electrocardiographic evidence of acute ischemia or active conduction system abnormalities. Prior to study entry, any ECG abnormality at screening must be documented by the investigator as not medically relevant.

- 3.1.9 The effects of IL-2 on the developing human fetus are unknown. For this reason and because chemotherapeutic agents are known to be teratogenic, women of child-bearing potential and men must agree to use adequate contraception (hormonal or barrier method of birth control; abstinence) prior to study entry and for the duration of study participation. Should a woman become pregnant or suspect she is pregnant while participating in this study, she should inform her treating physician immediately.
- 3.1.10 Ability to understand and the willingness to sign a written informed consent document.

3.2 Exclusion Criteria

Participants who exhibit any of the following conditions at screening will not be eligible for admission into the study.

- 3.2.1 Ongoing prednisone requirement >1 mg/kg/day (or equivalent).
- 3.2.2 Concurrent use of calcineurin-inhibitors plus sirolimus. Either agent alone is acceptable.
- 3.2.3 History of thrombotic microangiopathy, hemolytic-uremic syndrome or thrombotic thrombocytopenic purpura.
- 3.2.4 Exposure to any new immunosuppressive medication in the 4 weeks prior to enrollment.

CONFIDENTIAL

This document is confidential. Do not disclose or use except as authorized.

Phase II ECP and IL-2 for chronic GVHD

Version 2.0; August 15, 2016

3.2.5 Extra-corporeal Photopheresis (ECP) or rituximab therapy within 4 weeks prior to enrollment

3.2.6 Any contraindication to ECP, i.e. contraindication to heparin or 8-MOP.

3.2.7 Post-transplant exposure to any novel immunosuppressive medication (e.g., alemtuzumab) within 100 days prior to enrollment.

3.2.8 Donor lymphocyte infusion within 100 days prior to enrollment.

3.2.9 Active malignant relapse.

3.2.10 Active uncontrolled infection.

3.2.11 Inability to comply with IL-2 treatment regimen.

3.2.12 Uncontrolled cardiac angina or symptomatic congestive heart failure (NYHA Class III or IV: Appendix C; section 17.3).

3.2.13 Organ transplant (allograft) recipient.

3.2.14 HIV-positive individuals on combination antiretroviral therapy are ineligible because of the potential for pharmacokinetic interactions with the agents used after allogeneic HSCT. In addition, these individuals are at increased risk of lethal infections. Appropriate studies will be undertaken in participants receiving combination antiretroviral therapy when indicated.

3.2.15 Individuals with active hepatitis B or C are ineligible as they are at high risk of lethal treatment-related hepatotoxicity after HSCT.

3.2.16 Other investigational drugs within 4 weeks prior to enrollment, unless cleared by the Principal Investigator.

3.2.17 Pregnant women are excluded from this study because of the potential for teratogenic or abortifacient effects. Because there is an unknown but potential risk of adverse events in nursing infants secondary to treatment of the mother, breastfeeding should be discontinued.

3.3 Inclusion of Women, Minorities and Other Underrepresented Populations

We do not restrict study access for any participant based on gender, ethnicity or socioeconomic status.

CONFIDENTIAL

This document is confidential. Do not disclose or use except as authorized.

4. REGISTRATION PROCEDURES

4.1 General Guidelines for DF/HCC and DF/PCC Institutions

Institutions will register eligible participants with the DF/HCC Quality Assurance Office for Clinical Trials (QACT) central registration system. Registration must occur prior to the initiation of therapy. Any participant not registered to the protocol before treatment begins will be considered ineligible and registration will be denied.

A member of the study team will confirm eligibility criteria and complete the protocol-specific eligibility checklist.

Following registration, participants may begin protocol treatment. Issues that would cause treatment delays should be discussed with the Principal Investigator. If a participant does not receive protocol therapy following registration, the participant's protocol status must be changed. Notify the QACT Registrar of participant status changes as soon as possible.

4.2 Registration Process for DF/HCC and DF/PCC Institutions

The QACT registration staff is accessible on Monday through Friday, from 8:00 AM to 5:00 PM Eastern Standard Time. In emergency situations when a participant must begin treatment during off-hours or holidays, call the QACT registration line at [REDACTED] and follow the instructions for registering participants after hours.

The registration procedures are as follows:

1. Obtain written informed consent from the participant prior to the performance of any study related procedures or assessments.
2. Complete the protocol-specific eligibility checklist using the eligibility assessment documented in the participant's medical/research record. **To be eligible for registration to the study, the participant must meet each inclusion and exclusion criteria listed on the eligibility checklist.**

Reminder: Confirm eligibility for ancillary studies at the same time as eligibility for the treatment study. Registration to both treatment and ancillary studies will not be completed if eligibility requirements are not met for all studies.

3. Fax the eligibility checklist(s) and all pages of the consent form(s) to the QACT at [REDACTED]

CONFIDENTIAL

This document is confidential. Do not disclose or use except as authorized.

Exception: DF/PCC Affiliate sites must fax the entire signed consent form including HIPAA Privacy Authorization and the eligibility checklist to the Network Affiliate Office. The Network Affiliate Office will register the participant with the QACT.

4. The QACT Registrar will (a) validate eligibility, (b) register the participant on the study, and (c) randomize the participant when applicable.
5. The QACT Registrar will send an email confirmation of the registration and/or randomization to the person initiating the registration immediately following the registration and/or randomization.

4.3 General Guidelines for Other Participating Institutions

Please refer to Section 2.3 of the Data and Safety Monitoring Plan (Appendix I).

4.4 Registration Process for Other Participating Institutions

Please refer to Section 4.7 of the Data and Safety Monitoring Plan (Appendix I)

5. TREATMENT PLAN

Study therapy:

Each study participant will receive standard-of-care twice-weekly ECP for 16 weeks as per the transfusion medicine SOP. Briefly, ECP will be performed with the Therakos UVAR XTS or Cellex systems. Blood volume processed and 8-MOP dosing will be determined by subject hematocrit and blood volume per manufacturer guidelines. Clinical responders may continue ECP as standard-of-care after week 16, with or without extended-duration IL-2 therapy. If participants on ECP experience worsening of cGVHD requiring additional therapy prior to week 8, they may initiate low-dose IL-2 early, in consultation with the study PI.

After week 8, participants will initiate daily low-dose SC IL-2 (1×10^6 IU/m²/day) for self-administration for the remaining 8 weeks of ECP, i.e. from end of week 8-16. IL-2 will be typically administered on an outpatient basis. Expected toxicities and potential risks as well as dose modifications are described in Section 6 (Expected Toxicities and Dosing Delays/Dose Modification). Reference the extended-duration therapy section below for information concerning IL-2 therapy starting after Week 16.

CONFIDENTIAL

This document is confidential. Do not disclose or use except as authorized.

Phase II ECP and IL-2 for chronic GVHD

Version 2.0; August 15, 2016

Prednisone (or equivalent steroid) will be continued concomitantly with IL-2 without dose modification. Taper of prednisone will be permitted at the discretion of the treating physician if deemed in the participant's interest (e.g. steroid toxicity).

Of note, clinically stable cGVHD during taper of other immune suppression medications will be considered evidence of IL-2 efficacy; and progression of cGVHD during taper of other immunosuppressive therapy will not be considered evidence of IL-2 toxicity or lack of efficacy.

Reference Section 6.2 for instructions on dose modifications and delays of IL-2.

Extended-duration therapy:

After completing the 16 week study, patients experiencing clinical benefit (complete or partial response; as well as minor response not meeting NIH criteria for partial response) with an acceptable toxicity profile will be permitted to continue extended-duration IL-2 treatment indefinitely at the discretion of the treating physician. Restarting on extended-duration treatment can be delayed for only up to 2 weeks for justifiable clinical or administrative reasons. Longer delays in restarting treatment will have to be approved by the Principal Investigator. While on extended-duration IL-2, patients will be reassessed every 4 weeks to determine if IL-2 therapy should continue, at the discretion of the treating physician, who will document the rationale for the continued IL-2 therapy.

Toxicity data for extended-duration IL-2 will be collected on an ongoing basis and all treatment-related SAEs (per section 11.2) will be reported to the Principal Investigator and the IRB. Taper of other immune suppression medications during extended-duration IL-2 will be at the discretion of the treating physician. Addition of other cGVHD therapies to enhance response may be permitted for participants continuing on extended-duration therapy, at the discretion of the treating physician. While on extended-duration therapy, participants may have their dose modified in the event of toxicity per guidelines in Section 6.2 or at the discretion of the treating physician, in consultation with the Overall PI.

The required assessments for patients on extended-duration IL-2 therapy include:

- 1) Clinic visits locally or at study center for evaluation of toxicity and clinical benefit of IL-2 every 4 weeks (\pm 2 weeks). Required laboratory tests: CBC with differential; Serum Chemistries-glucose, BUN, creatinine, total bilirubin, alkaline phosphatase, AST, ALT, calcium.
- 2) Clinic visits at study center every 8 weeks (\pm 4 weeks). Required laboratory tests (in addition to above): immune assays that include quantitative serum immune globulins, plasma banking, and storage of additional mononuclear cells.

CONFIDENTIAL

This document is confidential. Do not disclose or use except as authorized.

Phase II ECP and IL-2 for chronic GVHD

Version 2.0; August 15, 2016

3) cGVHD assessments (Section 10.1) and cGVHD symptom score sheet every 16 weeks (\pm 4 weeks) until 1 year from the start of IL-2 treatment or the participant stops IL-2 therapy, whichever comes first.

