5.1 Pre-treatment Criteria

5.1.1 The following evaluations must be performed within four weeks prior to ECP for all patients

- Medical history and documentation of the rationale for treatment of the patient's disease (including steroid dose).
- Physical examination, including vital signs, weight, performance status.
- cGVHD assessment (Section 10.1)
- Pregnancy test for women of childbearing potential.
- Hematology: Complete blood count (CBC) with differential.
- Serum chemistries: glucose, BUN, creatinine, uric acid, total bilirubin, alkaline phosphatase, LDH, total protein, albumin, AST, ALT, and calcium.
- Thyroid function tests (TSH, T4, free T4).
- CMV viral load
- Quantitative serum immune globulins
- Immunology: plasma banking; and storage of additional mononuclear cells.

5.1.2 The following evaluations are required (except where indicated) within four weeks prior to ECP for patients with cGVHD involving specific organ systems

- Ocular examination with a Schirmer's test, for patients with ocular cGVHD (optional).
- Dermatologic assessment (\pm biopsy), for patients with cutaneous cGVHD.
- Oral examination (\pm biopsy), for patients with oral cGVHD (optional).

CONFIDENTIAL

This document is confidential. Do not disclose or use except as authorized.

Phase II ECP and IL-2 for chronic GVHD

Version 2.0; August 15, 2016

- Pulmonary function tests, for patients with pulmonary manifestations of cGVHD (within 4 weeks prior to treatment to 1 week after).
- Flexion assessment of affected joints, for individuals with contractures or musculoskeletal involvement related to cGVHD.

5.1.3 Evaluations during ECP and IL-2 treatment (End of Weeks 1, 2, 4, 6, 8, 9, 10, 12, 14), and off-study (End of Week 16)

- Medical history and clinical examination (including steroid dose, weeks 8 & 16).
- Drug diary review with member of study team (starting with IL-2 treatment).
- Toxicity assessment will be done on the same day as history and clinical examination.
- Hematology: CBC with differential.
- Serum chemistries: glucose, BUN, creatinine, uric acid, total bilirubin, alkaline phosphatase, LDH, total protein, albumin, AST, ALT, and calcium.
- CMV Viral load (or per institutional practice).
- Quantitative serum immune globulins (weeks 4, 8, 12, 16).
- Immunology: plasma banking; and storage of additional mononuclear cells (weeks 1, 2, 4, 6, 8, 9, 10, 12, 14, 16)
- Thyroid function tests (TSH, T4, free-T4) (week 16)

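### The only scheduled pregnancy test is tied to the start of ECP, so it is 56 to 84 days old at a planned week-8 first dose of IL-2

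*Combined protocol and SAP*

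**What the plan says.** Three parts of the protocol fix the timing.

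- **Start of the study drug.** Section 5 gives ECP for 16 weeks and brings in IL-2 for the second half: "After week 8, participants will initiate daily low-dose SC IL-2". If cGVHD worsens sooner and more therapy is needed, IL-2 may begin before week 8 after discussion with the study PI.
- **Pregnancy testing.** Section 5.1.1 opens with "The following evaluations must be performed within four weeks prior to ECP for all patients" and includes in its list "Pregnancy test for women of childbearing potential". Sections 5.1.3 and 5.1.4, which set out the on-treatment and week-8 and week-16 evaluations, list no pregnancy test. Table 2 in Section 9 marks the test in the baseline column only, not during therapy, at week 16 or during extended-duration IL-2.
- **Reason for excluding pregnancy.** Section 3.2.17 states: "Pregnant women are excluded from this study because of the potential for teratogenic or abortifacient effects". Section 3.1.9 says that the effect of IL-2 on a fetus is not known, and asks women of child-bearing potential and men to agree to contraception throughout participation. It adds: "Should a woman become pregnant or suspect she is pregnant while participating in this study, she should inform her treating physician immediately".

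Entry criteria are judged at screening. Section 3.1 begins "Participants must meet the following criteria on screening examination to be eligible to participate in the study".

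**The concern.** The pregnancy test is timed from ECP, the standard-of-care component, whereas the fetal-risk statement in 3.1.9 is about IL-2, which comes about two months later. A woman who tested negative at baseline could conceive during the ECP-only weeks, or could have been too early in pregnancy to test positive, and reach week 8 without suspecting it. Nothing scheduled at week 8 would show this before the first injection. She would then begin a daily drug whose fetal effects the protocol describes as unknown, and whose trial excludes pregnancy for that reason.

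What is at stake is an avoidable fetal exposure, at a visit where the participant is already examined and has blood drawn.

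**Working it through.** The plan gives no figure for the age of the test, so there is nothing to reproduce. The check is interval arithmetic plus a search of the schedule.

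**Inputs**
- Baseline test: 0 to 28 days before ECP starts (5.1.1).
- Planned IL-2 start: end of week 8 of ECP, 8 × 7 = 56 days (Section 5).
- Window for the week-8 visit: ±4 days (Table 2, footnote a).
- Expected participants: 25, of whom 10 are women (14.2.2, accrual table).

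**Age of the test at first IL-2 dose** = days from test to ECP + days from ECP to IL-2.

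| Case | Calculation | Age |
|---|---|---|
| Test on the day ECP starts | 0 + 56 | 56 days (8 weeks) |
| Test 28 days before ECP | 28 + 56 | 84 days (12 weeks) |
| Shortest, if IL-2 moves with the visit window | 0 + 56 − 4 | 52 days |
| Longest, if IL-2 moves with the visit window | 28 + 56 + 4 | 88 days |

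The last two rows assume that the first dose follows the week-8 visit wherever it falls in its window; the protocol does not say so.

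**Early start.** For IL-2 begun at the end of week *w*, the age is 7*w* to 7*w* + 28 days. At *w* = 4, for example, it is 28 to 56 days. The test is more recent than at week 8, but it still predates ECP.

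**Could another scheduled item detect a pregnancy before the first dose?**
- Week-8 visit (5.1.3, 5.1.4): history, examination, toxicity assessment, CBC, chemistries, CMV viral load, immune globulins and cGVHD assessment. None of these is a pregnancy test.
- Contraception agreement (3.1.9): lowers the chance of pregnancy but does not detect one.
- Self-report (3.1.9): works only if the woman knows or suspects.
- Treatment stopping criteria (5.4): pregnancy is not named. The clause on changes in the participant's condition would cover a known pregnancy, not an unsuspected one.
- Extra laboratory tests 4±2 days after IL-2 begins (Table 2 footnote): CBC, creatinine and LDH, after exposure and aimed at thrombotic microangiopathy.

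**Number of added tests.** One per woman of child-bearing potential who reaches IL-2: between 0 and about 10. The documents do not say how many of the 10 women are of child-bearing potential.

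**The case against.** The strongest reply is that ECP followed by IL-2 is one regimen. Eligibility is settled for all of it at entry, and the protocol requires contraception and prompt reporting for the whole of participation. The number affected could be zero. A single added test also leaves the following eight weeks of IL-2, and any extended-duration IL-2, on the same contraception and reporting rules.

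Much of this is fair. The safeguards in 3.1.9 are real, and the test does not replace them. The number of women concerned may be small or nil, in which case the cost is equally small. The test at first dose does not cover later conception. It does close the one interval in which a participant moves from no study drug to daily study drug on a test two to three months old.

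A reader might go further and infer that IL-2 starts at week 8 with no safety check, so that infection, renal function and thrombotic microangiopathy each need a formal start criterion. The documents do not support that. Examination, toxicity assessment, CBC and chemistries are repeated at weeks 1, 2, 4, 6 and 8. Sections 5.4 and 5.6 require removal for unacceptable or severe events and for a change in condition that the investigator judges disqualifying. Section 6.2 lets the physician withhold IL-2 for unrelated grade 3 non-hematologic toxicity. A renal cut-off at week 8 would also be stricter than 6.2, which sets no creatinine-clearance limit once IL-2 is running. For thrombotic microangiopathy, the exclusion in 3.2.3 concerns history at entry. These are matters of clinical judgment that the plan already provides for. An unsuspected pregnancy differs because no scheduled observation would bring it to the physician's attention.

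The study operations manual and Appendix I are cited but not supplied, and part of the protocol was not available for this review. A repeat test could be specified there. If so, 5.1.3 and Table 2 should still show it.

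**Conclusion.** The point holds for the pregnancy test. On the readable text, the only scheduled test is 56 to 84 days old at a planned week-8 IL-2 start (52 to 88 days if the start moves with the visit window), and more recent for an early start. First exposure to the study drug then depends on contraception and self-report, although fetal risk is the stated ground for excluding pregnancy.

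This rests on two assumptions: that IL-2 starts as planned at the end of week 8, and that no unsupplied document adds a test. The documents give no pregnancy rate and no count of women of child-bearing potential, so an expected number of exposed pregnancies cannot be calculated and none is claimed. The practical size is 0 to about 10 women.

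This is an inexpensive safety improvement. It does not show that participants start IL-2 unmonitored, and it has no bearing on the response rule of 17 of 25 or on its stated error rates.

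**What to change.** 1. In 5.1.3 and Table 2, add a pregnancy test for women of child-bearing potential at the week-8 visit, or immediately before IL-2 if it is started early.
2. In Section 5, require a negative result before the first IL-2 dose.

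**Cost.** A short amendment and at most about 10 tests. At week 8 the test can be run on blood already being drawn, so no extra visit is needed provided the result is available before the first injection; the ±4-day visit window should be used with that in mind. An early start that falls between scheduled visits may need its own sample. Rarely, a positive result would mean that IL-2 is withheld, which is the purpose of the test.
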